#### **6.5.2.6.** Adverse Events of Special Interest

#### **Incidence:**

Adverse event of special interest (AESI, for definition see Section 7.3), including hyperphosphatemia, will be summarized for each category/subcategory:

• Overall summary of AESI by worst CTC grade presented by category or subcategory / PT A by-patient listing of AESI will also be provided.

#### **Time to Onset:**

Time-to-onset of selected AESI, including hyperphosphatemia, will be graphically displayed for each category/subcategory of AESI using the Kaplan-Meier technique:

- Time to AESI
- Time to AESI of Grade >3

Summary statistics for time to onset on the patients who had AESI will also be provided.

#### **Time to Resolution:**

Time-to-resolution of selected AESI, including hyperphosphatemia, will be summarized separately for each category / subcategory:

- Time to resolution of AESI
- Time to resolution of AESI of Grade  $\geq 3$

Time-to-resolution analyses are restricted to treated patients who experienced the specific events.

The following summary statistics will be reported: percentage of subjects who experienced the specific events, percentage of subjects with resolution of the longest AESI, median time-to resolution and to  $\leq$  Grade 2 along with 95% CI (derived from Kaplan-Meier estimation, if estimable) and ranges.

#### **6.5.2.7.** Multiple Adverse Events

The following summary tables will be provided:

- Total number and rate (exposure adjusted) of occurrences for all AEs.
- For AESI: number of subjects experiencing an AESI once or multiple times

The exposure adjusted incidence rate per X patient time is calculated as  $X \times Y \times$  (total number of unique AEs)/(total exposure time), where:

X = user-specified time factor, X = 1000 or 100

Y = 365.25 for years or Y = 30.4375 for months

Listing displaying the unique instances of all AEs (that is, after duplicates have been eliminated and overlapping and contiguous occurrences of the same event (same PT) have been collapsed) will be provided.

Serum chemistry	AST, ALT, ALP, total bilirubin, glucose, creatinine clearance, blood ured nitrogen (BUN) or urea, phosphorus, calcium, chloride, sodium, potassium creatine kinase (CK), creatinine kinase MB (CK-MB), Troponin I, Troponin T	
Urinalysis	Urine protein, glucose	
Other	CCI	

- · Neutrophils includes both segmented and band neutrophils
- · creatinine clearance includes calculated (Ccr) or measured creatinine clearance

#### **Additional Analysis**

In addition, further analyses on specific laboratory parameters will be performed:

# Abnormal Hepatic Function Test

The number of subjects with the following laboratory abnormalities from on-treatment evaluations will be summarized by treatment group:

- ALT or AST > 3 x ULN, > 5 x ULN, > 10 x ULN and > 20 x ULN
- Total bilirubin > 2 x ULN
- Concurrent (within 1 day) ALT or AST > 3 x ULN and total bilirubin > 2 x ULN
- Concurrent (within 30 days) ALT or AST > 3 x ULN and total bilirubin > 2 x ULN

The following scatterplots will be produced for the following hepatic laboratory parameters:

- Total bilirubin peak vs. AST peak
- Total bilirubin peak vs. ALT peak

On-treatment peak total bilirubin and on-treatment peak AST/ALT may or may not happen on the same day of liver testing.

A by-subject listing of these specific abnormalities will be provided.

#### 6.5.3.1.1. Ophthalmological Examination

Ophthalmological examination is performed at screening (within 28 days prior to study medication administration on Day 1 of Cycle 1), 4-6 weeks after starting treatment with TAS-120, End of treatment visit. Ophthalmological examination results will be summarized and listed.

### 6.5.3.1.2. Neurological Examination

The neurological examination is obtained at screening within 28 days prior to TAS-120 administration on Day 1 of cycle 1, other time due to local requirements or physician judgement, end of treatment visit, and 30-day safety follow-up visit. The examination results will be summarized and listed.

#### 6.5.4. Vital Signs

Vital sign measurements including systolic blood pressure, diastolic blood pressure, pulse rate, respiration rate, and temperature at each scheduled and changes from baseline in vital sign measurements will be summarized with descriptive statistics at each scheduled time point.

Weight at each scheduled time and changes from baseline will be summarized with descriptive statistics at each scheduled time point for the safety population. Weight will be displayed in kilograms, height, collected only at baseline, will be displayed in centimeters, and temperature will be displayed in Celsius. The safety population will be used.

All vital signs data will be presented in a listing.

# **6.5.5.** Electrocardiograms

Descriptive statistics for ECG parameters and changes from baseline will be presented by visit and treatment group (and/or dose).

Shift tables will present changes from baseline in ECG interpretation (categorized as normal; abnormal, not clinically significant; and abnormal, clinically significant) to end of treatment (or end of phase or by visit).

In addition, the number (percentage) of patients with at least 1 post-baseline abnormal ECG result in QTc Fridericia during the on-treatment period will be summarized. Clinically abnormal ECG results based on QTc Fridericia correction will be categorized as follows:

Absolute QTcF interval prolongation:

- QTc interval <= 470 ms
- QTc interval >470 480 ms
- QTc interval > 480 500 ms
- QTc interval > 500 ms

Change from baseline in QTcF interval:

- QTC interval increases from baseline <= 30 ms
- QTC interval increases from baseline 30 60 ms
- QTC interval increases from baseline > 60 ms

The number patient who experienced QTc abnormalities during the post baseline, but not presented in the baseline measurements will be summarized.

A subject level listing of ECG will be provided.

#### 6.5.6. Physical Examination

All physical examination is performed 24 hours prior to TAS-120 administration on day 1 beginning with cycle 2. The baseline screening measurement of physical examination will be taken on screening within 28 days prior to TAS-120 administration on Day 1 of Cycle 1. The physical examination will also obtain at the End of Treatment Administration, and 30-day safety follow-up visit.

The physical examination data will be presented in a patient level listing.

#### **6.5.7. ECOG Performance Status**

The ECOG performance status score will be obtained at the following time points: screening, and 24 hours prior to TAS-120 on day 1 beginning with cycle 2, the End of Treatment Administration, and 30-day safety follow-up visit. The ECOG performance status scores and the grades from 0 to 5 are described in the following table:

Table 11. Grade Categories of Eastern Cooperative Oncology Group Score

GRADE	ECOG
0	Fully active, able to carry on all pre-disease performance without restriction.
1	Restricted in physically strenuous activity but ambulatory and able to carry out work of a light or sedentary nature, eg, light house work, office work.
2	Ambulatory and capable of all self-care but unable to carry out any work activities. Up and about more than 50% of waking hours.
3	Capable of only limited self-care, confined to bed or chair more than 50% of waking hours.
4	Completely disabled. Cannot carry on any self-care. Totally confined to bed or chair.
5	Dead.

The change from day 1 in cycle 1 in the ECOG performance status scores will be presented in a shift table. Time to Deterioration of ECOG performance status to 2 or greater will be summarized. A patient level listing will also be presented.

# 6.5.8. Pregnancy Test

For female patients with child bearing potential, pregnancy test result will be listed.

#### **6.5.9.** Tumor Tissue Sample Collection

The archived formalin fix paraffin embedded (FFPE) tumor tissue samples will be collected at any time while on the study from patients who signed the ICF if available. A patient level listing will be produced to display the FFPE output.

# 6.6. Patient Reported Outcomes (PRO)

Unless otherwise specified, the primary timepoint for the analysis of PRO endpoints is the last analysis visit before data is missing for more than 50% of the PRO population. This 'censoring' is done since when there is more than 50% missing data, reported PRO scores will be very sensitive to missing data assumptions. The primary assessment timepoint for the PRO analysis will be determined based on a data review prior to the database lock.

All EQ-5D and EORTC-QLQ-C30 questionnaires completed at baseline and on-study will be assigned to a time-point according to the windowing criteria in Table 12 and included in the analysis. In case a patient has two on-study assessments within the same window, the assessment closest to the time-point will be used. And, in the case of two assessments at a similar distance to the time-point, the latest one will be chosen. In the event where the patient has no assessment at all in a specific window, the observation will be treated as missing for that time-point.

Table 12. Time Windows for EQ-5D and EORTC-QLQ-C30 Assessment

Nominal Time-Point	Time Window
Screening	-28 to -1 days
Cycle 2, Cycle 4	Day $1 \pm 3$ days
>Cycle 4	Every 3 cycles on day 1 of the cycle $\pm$ 7 days
End of Treatment	Within 3 days of the decision to discontinuation

The Patient-Reported Outcomes (PRO) will be evaluated as close as possible to the tumor assessment schedules.

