9. STUDY PROCEDURES

The study assessments are described by procedure in the following sections. All information required by the protocol must be recorded.

The study schedule must be followed; however, in unavoidable circumstances (e.g., holidays, weekends, etc.) a window of ± 3 days is allowable for study procedures as long as the proper order of procedures and assessments is maintained. The ± 3 -day window does not apply to assessments on Day 1 of Cycle 1.

For computed tomography (CT) scans, a window of ± 2 weeks (up to Cycle 4) or ± 7 days (all subsequent cycles) is allowable. These windows are not applicable during Screening. If any Screening assessments are repeated on Day 1 of Cycle 1 pre-dose, the site must ensure the patient meets the eligibility criteria listed in [Section 7.2](#), Study Population prior to the patient taking the first dose of TAS-120.

Note: Procedures performed during screening period within 72 hours prior to dosing on C1D1 do not need to be repeated on C1D1.

9.1. Pre-screening of Tumor Tissue Sample for FGFR2 Gene Fusions or other FGFR2 Rearrangements in Patients with iCCA (Phase 2 Only)

Archived or fresh tumor tissue biopsy samples will be tested for FGFR2 gene fusions or other FGFR2 rearrangements prior to enrolling patients to the Phase 2 part of the study.

Patients can be enrolled and treated based on the following:

- a. Testing by Foundation Medicine:
 - i. Sent to Foundation Medicine as part of study pre-screening; or
 - ii. Already tested by Foundation Medicine; in this case, it is requested that tumor tissue be sent to Foundation Medicine if available.
- b. Local laboratory testing using next generation sequencing [NGS], fluorescence in situ hybridization [FISH], or other assays that can determine FGFR2 gene fusions or other FGFR2 rearrangements on tumor tissues or from ctDNA. It is requested that patients enrolled on this basis provide tumor tissues to Foundation Medicine, if available from either archival samples or fresh tumor biopsy.

Testing may be performed at any time prior to enrollment into the study. -Results from the testing if not done as part of the TAS-120-101 protocol, must be maintained in the source files at the site.

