9.18. Patient-Reported Outcomes

Two Patient-Reported Outcome (PRO) instruments, EuroQol-5D measure of health-related quality of life (EQ-5D) and the European Organization for Research and Treatment of Cancer Quality of Life Questionnaire (EORTC QLQ-C30) will be used in the Phase 2 part of the study. EQ-5D is a standardized measure of health status as patient-reported outcome assessment. EORTC QLQ-C30 is an integrated system for assessing the health-related quality of life of cancer patients participating in international clinical trials. These assessments will be collected at the following time points (as close as possible to the time points when tumor assessment is performed):

- Screening within 28 days prior to Day 1 of Cycle 1.
- At the end of every 2 cycles (up to +2 weeks), up to Cycle 4.
- Following Cycle 4, at least after every 3 cycles (\pm 7 days) or as clinically indicated.
- At end of treatment (EOT)

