# 15 October 2020

		Screening Period	Treatment Period (1 cycle = 21 days)				Safety Follow-up		Follow-	Notes			
	Duo	Dna	Pre-	Dna	(Within 28 Days	Cycle 1			Cycles ≥2	End of Tx (+0-7 days)	days Last	-	
	Screening	Prior to First	Day				Day	1 of -7 da	(±3) er	Survival up Period			
		Dose)	1	4 (±1d)	8 (±3d)	15 (±3d)	1 (±3d)	End (+0-	30 (±3 After	on Jan			
12-Lead Electrocardiogram		x	X				X	X	X		At screening and 2 hours (±15 minutes)  after dosing on D1 of each cycle.		
Hematology and coagulation		x	x		x	X	x	X	X		Within 24 hours prior to treatment on D1 of each cycle, any time on C1D8 and C1D15, and as clinically indicated.		
Chemistry (Serum or plasma)		x	x	(X)	x	х	x	X	x		Within 24 hours prior to treatment on D1 of each cycle, any time on C1D8 and C1D15, and as clinically indicated. Additional collection for phosphorus only at C1D4.		
Urinalysis (Urine dipstick)		X	X				X	X	X				
Pregnancy test		x	x				x	X	x		Serum pregnancy test required for WOCBP at screening and end of treatment; serum or urine pregnancy test required at all other timepoints.		
Blood PK Sampling (Required)							x				Blood samples (1 mL) collected C2D1 pre-dose and at 1h and 3h (±30 min) post-dose. Additional samples collected pre-dose on C3D1 and C4D1.		
ctDNA blood samples		x						(X)			Minimum of 20 mL whole blood at screening (mandatory) and EOT (optional).		
CCI													
Prior & concomitant medications, AE assessments	х	x					→	x	x		Collect from the time main informed consent is signed through 30 days after administration of the last dose of TAS-120 or until the start of new anticancer therapy, whichever is earlier. AEs directly associated with a pre-screening procedure should be reported as described in Protocol Section 12.1		

		Screening Period	Treatment Period (1 cycle = 21 da	ıys)	Safety Follow-up	Follow-	Notes
	Pre-	(Within 28 Days	Cycle 1	Cycles ≥2	of Tx days) () days Last		
	Screening	Prior to First Dose)	Day  1	Day 1 (±3d)	End of Tx (+0-7 days) 30 (±3) days After Last	Survival up Period	
PRO (EQ-5D and EORTC QLQ-C30)		X	1 (±1d) (±3d) (±3d)	X	X	S. 1	Evaluated at screening and as close as possible to the tumor assessment schedule: at the end of every 2 cycles (up to +2 weeks) through Cycle 4 and every 3 cycles (±7 days) thereafter until disease progression or initiation of new anticancer therapy (whichever is first).

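### The Phase 2 SAP's analysis windows for the patient-reported outcomes (Table 12) do not match the schedule on which the questionnaires are collected

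*SAP*

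**What the plan says.** **Collection.** Protocol 9.18 schedules both questionnaires "At the end of every 2 cycles (up to +2 weeks), up to Cycle 4", then after every three cycles with ±7 days, and at end of treatment. The PRO row of Table 1 in the Phase 2 SAP repeats this: "at the end of every 2 cycles (up to +2 weeks) through Cycle 4 and every 3 cycles (±7 days) thereafter". Protocol 9.19 allows the end-of-treatment visit 0–7 days after the decision to stop.

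**Analysis.** Section 6.6 of the Phase 2 SAP maps questionnaires to time points through Table 12:

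- Cycle 2 and Cycle 4: Day 1 ±3 days.
- After Cycle 4: "Every 3 cycles on day 1 of the cycle $\pm$ 7 days".
- End of treatment: "Within 3 days of the decision to discontinuation".

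For any other outcome, "where the patient has no assessment at all in a specific window, the observation will be treated as missing" for that time point. The primary PRO time point is "the last analysis visit before data is missing for more than 50% of the PRO population", and "The primary assessment timepoint for the PRO analysis will be determined based on a data review prior to the database lock".

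**The concern.** Table 12 places the first two post-baseline time points at the start of Cycles 2 and 4, whereas the questionnaires are collected at the end of those cycles. A questionnaire completed exactly on schedule would then fall outside every scheduled-visit window and be counted as missing. The row for later visits does not say from which cycle to count, so two programmers could build different data sets. The end-of-treatment row is narrower than the visit it is meant to capture.

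At stake are the by-visit change scores, the shift summaries and the 10-point deterioration percentages, together with the primary PRO time point, which is itself chosen by the amount of missing data. If missingness is created by the windows, the 50% rule responds to a programming artefact and not to patient attrition.

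**Working it through.** **Inputs.** Cycles are 21 days without breaks (Protocol 8.1.2). Collection timing is from Protocol 9.18 and Phase 2 SAP Table 1, the end-of-treatment timing from Protocol 9.19, and the analysis windows from Phase 2 SAP Table 12.

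**Formulas.** Day 1 of Cycle k is study day 21(k − 1) + 1. The end of Cycle k is study day 21k.

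**Cycles 2 and 4 as written.**

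- Cycle 2 Day 1 = 21 × 1 + 1 = 22, so the window is days 19–25. The end of Cycle 2 is day 42, so collection is days 42–56.
- Cycle 4 Day 1 = 21 × 3 + 1 = 64, so the window is days 61–67. The end of Cycle 4 is day 84, so collection is days 84–98.

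**Later visits.** The first is at the end of Cycle 7, day 147 ± 7, or days 140–154.

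- Anchored at Cycle 7 Day 1 (day 127), the window is days 120–134.
- Anchored at Cycle 8 Day 1 (day 148), it is days 141–155.

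| Time point | Permitted days | Table 12 window | Days in common |
|---|---|---|---|
| End of Cycle 2 | 42–56 | 19–25 | 0 of 15 |
| End of Cycle 4 | 84–98 | 61–67 | 0 of 15 |
| End of Cycle 7, anchor Cycle 7 | 140–154 | 120–134 | 0 of 15 |
| End of Cycle 7, anchor Cycle 8 | 140–154 | 141–155 | 14 of 15 |
| End of treatment (days after decision) | 0–7 | 0–3 | 4 of 8 |

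The end of Cycle 10 gives the same split: permitted days 203–217; anchor Cycle 10 (183–197) 0 of 15, anchor Cycle 11 (204–218) 14 of 15. If the later row were started at Cycle 5 (Day 1 = 85, window 78–92), it would take 9 of the 15 end-of-Cycle-4 days (84–92) and label them as a later visit.

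**Variants for Cycles 2 and 4.**

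- *Table 12 means Day 1 of the following cycle.* Cycle 3 Day 1 = 43 (window 40–46) and Cycle 5 Day 1 = 85 (window 82–88). Each covers 5 of 15 permitted days (42–46 and 84–88).
- *The ±2-week allowance in Protocol 9 applies.* It is stated for CT scans up to Cycle 4 and conflicts with the one-sided two weeks elsewhere. Permitted days become 28–56 and 70–98. The literal overlap is 0 of 29 each; on the following-cycle reading it is 7 of 29 each.
- *The general ±3-day allowance in Protocol 9 is added to the schedule.* Permitted days become 39–59 and 81–101. The literal overlap is 0 of 21 each.
- *Both allowances are stacked (−17 to +17 days).* One edge day each is shared, day 25 and day 67, out of 35.

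A dose delay moves Day 1 of a cycle and the end of that cycle together, so it creates no overlap.

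**Effect on the primary time point.** On the literal reading almost every patient is missing at the first post-baseline visit, so the last visit before missingness passes 50% is screening.

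**The case against.** The strongest reply is that Table 12 contains a labelling slip. In both schedule tables the PRO mark sits under a generic column for Day 1 ±3 of Cycle 2 onward. That is the likely origin of the wording, and an end-of-Cycle-2 questionnaire would naturally be completed at the Cycle 3 Day 1 visit. Read that way throughout, the rows become Cycle 3, Cycle 5, Cycle 8, Cycle 11 and so on, and the later visits fit well (14 of 15 days). This is plausible, but it is not what the table says. It still leaves Cycles 2 and 4 with 5 of 15 permitted days, or 7 of 18 if a 3-day lead is also allowed (40–46 against 39–56).

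SAP 6.6 also says that every completed questionnaire will be assigned to a time point and analysed. That does not rescue the table; it makes the section contradict itself, because the windows cannot deliver it. A pre-lock data review would probably notice two empty visits, but as written it selects the time point and has no stated power to alter the windows.

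Several limits stand:

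- Two weeks is a tolerance and not a uniform spread of dates. If most questionnaires were completed close to Day 1 of the next cycle, losses on that reading could be modest.
- The ±2-week variant is stated for CT scans only, and a Cycle 5 start is a strained reading.
- Membership of the PRO population does not depend on Table 12. Deterioration percentages use patients assessed at each visit, so what is lost is numbers, not the definition of the denominator.
- PROs are other-secondary, single-arm and descriptive.

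**Conclusion.** The concern holds. As written, the Cycle 2 and Cycle 4 windows contain none of the permitted collection days, and this survives each single alternative window for collection. The row for later cycles gives 0 or 14 of 15 days depending on an unstated anchor, and the end-of-treatment row covers half its visit window. Followed literally, the plan marks on-schedule questionnaires as missing at the first two post-baseline visits and yields no usable post-baseline primary PRO time point.

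The figures assume undelayed 21-day cycles and count calendar days. The documents give no distribution of questionnaire dates, so the share of patients lost on the following-cycle reading is unknown. ORR, the by-patient listings and, as far as the SAP defines it, time to deterioration are not affected. It should be corrected before lock, but it does not threaten the trial's main conclusion.

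**What to change.** Before database lock, replace Table 12 with windows anchored to the end of each patient's actual cycle, so that delays do not push visits out of window:

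- **End of Cycle 2 and end of Cycle 4:** 3 days before to 14 days after (nominally days 39–56 and 81–98). If the ±2 weeks in Protocol 9 is confirmed as governing, use 14 days either side (nominally 28–56 and 70–98, which do not overlap).
- **End of Cycle 7 and every third cycle after it:** ±7 days (nominally day 147 and every 63 days).
- **End of treatment:** 0–7 days after the decision to discontinue.

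Contiguous windows would be an alternative, and would fit better with the stated aim of using every questionnaire. Splitting at the midpoints between nominal days 1, 42, 84, 147 and 210 (21.5, 63, 115.5 and 178.5) gives days 22–63, 64–115 and 116–178.

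Under any scheme, state which time point takes an end-of-treatment questionnaire that also falls in a scheduled window. State also how to treat one completed when Protocol 9.20 replaces the end-of-treatment visit with the 30-day visit. Then apply the 50% rule.

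The cost is one SAP table and the visit-mapping program. No data collection changes.

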#### 6.6.1. EO-5D

PRO endpoints relating to the EQ-5D are as follows:

- Shift from screening in the EQ-5D 5 dimensions
- Change from screening in the EQ-5D-3L Index
- Change from screening in the EQ-5D-3L VAS score

There are 5 dimensions: mobility, self-care, usual activities, pain/discomfort and anxiety/depression in EQ-5D questionnaire. Each dimension has 3 levels: no problems, some problems, severe problems (EQ-5D-3L). Once the data have been collected and a database created, a scoring function can be used to assign a value (i.e., EQ-5D index score: 5 dimensions digits combined in a 5-digit number) to self-reported health states from a set of population-based preference weights.

The EQ VAS records the patient's self-rated health state on a 100-point vertical, visual analogue scale (0 = worst imaginable health state; 100 = best imaginable health state).

A by-patient listing of EQ-5D with the problem levels for each of the 5 dimensions (mobility, self-care, usual activities, pain/discomfort and anxiety/depression), EQ-5D Index and EQ-VAS will be provided.

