12.2.2.6. Patient-Reported Outcomes

The analyses of EQ-5D and EORTC QLQ-C30 will be performed in all treated patients who have an assessment at baseline and at least one subsequent assessment.

EQ-5D

Patient's overall health state on a visual analog scale (EQ-VAS) at each assessment time point will be summarized using descriptive statistics. Proportion of patient's reporting problems for the 5 EQ-5D dimensions at each assessment time point will be summarized by level of problem. Percentages will be based on number patients assessed at each assessment time point.

A by-patient listing of EQ-5D with the problem levels for each of the 5 dimensions (mobility, self-care, usual activities, pain/discomfort and anxiety/depression), health state (5 dimensions digits combined in a 5-digit number) and EQ-VAS will be provided.

EORTC QLQ-C30

All scales and single items are scored on a categorical scale and linearly transformed to 0-to-100 scales with higher scores for a functional scale representing higher levels of functioning, higher scores for the global health status/quality of life representing higher levels of global health status/quality of life, and higher scores for a symptom scale representing higher level of symptoms.

Baseline and change from baseline in EORTC QLQ-C30 global health status/quality of life (QoL) composite scale data and the remaining EORTC QLQ-C30 scale data will be summarized by time point using descriptive statistics for each cohort. In addition, the percentage of patients demonstrating a clinically meaningful deterioration (defined as a 10-point change from baseline) will be presented for each scale at each assessment time point. Percentages will be based on number patients assessed at each assessment time point.

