#### EQ-5D

The EQ-5D descriptive system comprises the following 5 dimensions: mobility, self-care, usual activities, pain/discomfort and anxiety/depression. Each dimension has 3 levels: no problems, some problems, severe problems. Once the data have been collected and a database created, a scoring function can be used to assign a value (i.e., EQ-5D index score) to self-reported health states from a set of population-based preference weights.

The EQ VAS records the patient's self-rated health state on a 100-point vertical, visual analogue scale (0 = worst imaginable health state; 100 = best imaginable health state).

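### Phase 2 SAP 6.6.1 describes the EQ-5D index in two incompatible ways, and no value set is named, so the planned change score has no settled derivation

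*SAP*

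**What the plan says.** Section 6.6.1 of the Phase 2 SAP lists three EQ-5D outputs: shifts in the five dimensions, change in the VAS score, and "Change from screening in the EQ-5D-3L Index". The instrument is the three-level version: "Each dimension has 3 levels: no problems, some problems, severe problems (EQ-5D-3L".

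The same section then explains the index. It says that "a scoring function can be used to assign a value", and in parentheses identifies that value as "EQ-5D index score: 5 dimensions digits combined in a 5-digit number". The sentence continues after the parenthesis by saying that the value is given "to self-reported health states from a set of population-based preference weights".

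Two other places bear on this:

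- SAP Section 3.2.2, under EQ-5D, has almost the same sentence, but its parenthesis stops at the name of the score: "EQ-5D index score) to self-reported health states from a set of population-based preference weights". There is no 5-digit number.
- Protocol Section 12.2.2.6 has the 5-digit wording attached to a different noun: "health state (5 dimensions digits combined in a 5-digit number". It is one of the items in the by-patient listing. The protocol plans no analysis of an index.

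Neither document names a value set, tariff or country of origin for the weights.

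**The concern.** A 5-digit EQ-5D code identifies which level was reported on each dimension. It is a label, and the size of the number has no meaning as a quantity of health. A preference-weighted index is a single value on which differences can be taken and averaged. The SAP plans to take differences, so it matters which of the two a programmer derives.

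Section 6.6.1 is the analysis section, and its parenthesis points to the label. If that wording were followed, the change score would depend on which column a digit sits in. If the preference-weight wording were followed, the result would be interpretable, but the value set would have to be chosen outside the plan, possibly after the data have been seen. Change in index is an endpoint that the SAP adds to the protocol's EQ-5D plan, so the protocol offers no derivation to fall back on.

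**Working it through.** No sample-size, power or alpha figure in the plan depends on this point, so there is no stated figure to reproduce. The check has two parts.

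**1. The three descriptions side by side**

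| Place | What the 5-digit number is | What the index is |
|---|---|---|
| Protocol 12.2.2.6 | The health state, in a listing | Not mentioned |
| SAP 3.2.2 | Not mentioned | A preference-weighted value |
| SAP 6.6.1 | The index (parenthesis) | A preference-weighted value (rest of the sentence) |

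A concatenated code needs no weights, so the two halves of the 6.6.1 sentence conflict. The listings point to the likely origin. The protocol lists the dimension levels, the health state and the EQ-VAS; the SAP lists the dimension levels, the index and the EQ-VAS. It appears that the protocol's description of the health state was carried over to the index.

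**2. What the literal parenthesis would produce**

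Inputs: five dimensions in the order mobility (M), self-care (S), usual activities (U), pain/discomfort (P), anxiety/depression (A), with three levels each, from SAP 6.6.1. Assumption: levels are coded 1, 2, 3, with 3 the worst.

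Code = 10,000·M + 1,000·S + 100·U + 10·P + A. There are 3^5 = 243 possible states, from 11111 to 33333.

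A one-level worsening from 11111:

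- mobility: 21111 − 11111 = +10,000
- self-care: 12111 − 11111 = +1,000
- usual activities: 11211 − 11111 = +100
- pain/discomfort: 11121 − 11111 = +10
- anxiety/depression: 11112 − 11111 = +1

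A patient moving from 13333 to 21111 improves by two levels on four dimensions and worsens by one level on mobility. The code changes by 21111 − 13333 = +7,778, in the direction of worse health.

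If the five dimensions varied equally and independently, mobility's share of the variance of the code would be 10^8 / (10^8 + 10^6 + 10^4 + 10^2 + 1) = 100,000,000 / 101,010,101 = 0.99.

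Over all ordered pairs of the 243 states whose level sums differ (50,096 pairs), the code and the level sum rank the two states in opposite order in 11,920, which is 11,920 / 50,096 = 23.8%. The level sum serves here only as a crude yardstick of overall severity.

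On the preference-weight reading no number can be computed, because the weights are not given.

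**The case against.** The strongest reply is that the SAP does not really intend to subtract codes. The main clause of the 6.6.1 sentence refers to a scoring function and preference weights, Section 3.2.2 describes the index in those terms only, and the protocol labels the 5-digit number correctly. Taken together, the texts suggest a drafting slip that an experienced programmer would notice. The other two EQ-5D outputs, the dimension shifts and the VAS change, do not depend on the index at all.

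Most of this stands. A reader might infer from the parenthesis that the plan has settled on arithmetic with health-state codes and that the planned change score is therefore meaningless. The documents do not support that: they contradict themselves, and the preference-weight wording is as explicit as the code wording.

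The reply does not make the derivation usable. Sections 3.2.2 and 6.6.1 say only that a scoring function may be applied, and neither identifies one. The code is the only version of the index that could be computed from the text as it stands. By contrast, SAP Section 6.6.2 gives item-level formulas for every QLQ-C30 scale and a rule for missing items.

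**Conclusion.** The point holds as an internal contradiction together with an omission. The parenthesis in SAP 6.6.1 misdescribes the index and conflicts with the rest of its own sentence and with Section 3.2.2. The preference-weighted definition that remains is incomplete, because no value set is named.

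The figures of +10,000 against +1, the 99% variance share and the 23.8% of discordant pairs describe what would follow only if the parenthesis were programmed literally, with levels coded 1 to 3 in the listed order. The variance share also assumes equal and independent variation across dimensions. They show that the literal reading is unusable; they do not predict what the trial will report.

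The consequence is small. It concerns one descriptive secondary patient-reported output in a single-arm phase, with no hypothesis test attached. ORR, the sample size and alpha are unaffected.

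**What to change.** In SAP 6.6.1:

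1. Delete the 5-digit wording from the index definition and define the index as the preference-weighted EQ-5D-3L value, in line with Section 3.2.2.
2. Name the value set before database lock and say how it applies across the SAP's regions (North America, Europe, Asia Pacific excluding Japan, and Japan). One set for all patients and country-specific sets are both possible; the documents do not settle this, so the sponsor should choose and record the choice.
3. Keep the 5-digit number only as the health-state profile in the by-patient listing, as Protocol 12.2.2.6 has it, with the index shown separately.

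The cost is a sentence or two in the SAP and a matching line in the listing specification. No new data are needed, because the value is derived from dimension responses already collected.
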